## 7. SAFETY ASSESSMENT

Given that the intervention in this study utilizes a low-risk product in accordance with its intended use and labeling, the safety risk to participants is minimal. Participants will be routinely monitored as they will be in the acute-care setting during the study, and will have their perineum and meatus inspected regularly for any signs of irritation. Adverse Events, as described below, will be collected for all participants and reviewed by the PI.

### 7.1. Adverse Events and Serious Adverse Events

During this study, the ReadyCleanse® cloth will be used in accordance with its labeling and intended use, presenting minimal risk to the participants. Consequently, the definitions for Adverse Events and Serious Adverse Events listed below will be used in the course of this study.

#### 7.1.1. Definition of Adverse Events (AE)

If the condition of the participant's perineal skin and soft-tissue deteriorates *unexpectedly*, per the PI's interpretation, or if there is a new condition that the PI determines is not related to the baseline health condition *but could be* related to the use of the study product, it will be recorded as an AE.

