#### 7.2.2. Relatedness of Event

All adverse events (AEs) must have their relationship to study intervention assessed by the PI who examines and evaluates the participant based on temporal relationship and his/her clinical judgment. The degree of certainty about causality will be graded using the categories below.

- **Unrelated:** This category applies to those adverse events which, after careful consideration, are clearly and incontrovertibly due to extraneous causes (disease, environment, etc.)
- **Possible:** This category applies to those adverse events for which, after careful medical consideration at the time they are evaluated, a connection with the Investigational Product administration appears unlikely but cannot be ruled out with certainty.
- **Probable:** This category applies to those adverse events which, after careful medical consideration at the time they are evaluated, are felt with a high degree of certainty to be related to the Investigational Product.
- **Definite:** This category applies to those adverse events which, after careful consideration, are clearly and incontrovertibly due to the Investigational Product.

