#### 7.2.3. Expectedness

The PI will be responsible for determining whether an AE is expected or unexpected. An AE will be considered unexpected if the nature, severity, or frequency of the event is not consistent with the risk information previously described for the study intervention. One AE that may occur during the study is mild irritation at the cleansing site.

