#### 7.2.4. Relatedness of Event Time Period & Frequency of Event Assessment and Follow-Up

All AEs and SAEs will be captured on the appropriate reporting form. Information to be collected includes event description, time of onset, clinician's assessment of severity, relationship to study product (assessed only by those with the training and authority to make a diagnosis), and time of resolution/stabilization of the event. All AEs and SAEs as defined in section 7.1 occurring while on study must be documented appropriately regardless of relationship. All AEs will be followed to adequate resolution.

Changes in the severity of an AE will be documented to allow an assessment of the duration of the event at each level of severity. Changes in severity will necessitate a new CRF to document the new level of severity. AEs characterized as intermittent require documentation of onset and duration of each episode.

The PI will record all reportable events with start dates occurring any time after the start of the Educational Intervention through the end of the study or resolution of the AE/SAE, whichever is later.

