	 Related (event definitely related to IP, as judged by the Principal Investigator)
Action Taken with Investigational Product:	 Discontinued- Please Provide Date:
	 Interrupted- Please Provide Date:
	 None

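### The AE definition in Section 7.1.1 screens on expectedness or causality before recording, so some perineal skin worsening may go unrecorded; separately, the SAE form has no Probable category

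*Combined protocol and SAP*

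**What the plan says.** Section 7.1.1 admits an event as an AE by either of two routes, joined by an or.

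- Route 1: the participant's "perineal skin and soft-tissue deteriorates *unexpectedly", in the investigator's interpretation. No causal condition is attached.
- Route 2: there is "a new condition that the PI determines is not related to the baseline health condition" but that could be related to the product. No expectedness condition is attached.

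The rest of Section 7 handles the same two judgements as later steps. Section 7.2.2 grades relatedness in four categories, the lowest being for events that "are clearly and incontrovertibly due to extraneous causes". Section 7.2.3 has the investigator class each AE as expected or unexpected, and gives an example: "One AE that may occur during the study is mild irritation at the cleansing site". The AE form in Appendix 11.3 has Expected and Unexpected boxes and a Not Related code. Section 7.2.4 adds: "All AEs and SAEs as defined in section 7.1 occurring while on study must be documented appropriately regardless of relationship".

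The SAE form in Appendix 11.4 offers three relatedness choices: Not Related, Possibly Related, and Related. The last is explained as "event definitely related to IP, as judged by the Principal Investigator".

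**The concern.** The definition works as a gate. Section 7.2.5 puts on the AE form only what meets Section 7.1.1, and Section 7.1.2 builds the SAE definition on the AE definition. An event stopped at the gate gets no form, no severity grade, no relatedness grade, no 48-hour report and no sponsor evaluation under Section 7.2.6. The judgement that stops it is the investigator's alone and leaves no AE record for others to check.

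Section 7 says the perineum and meatus will be inspected regularly for irritation, so findings will be made that have to pass this gate. AE review is also a listed ground for suspension in Section 9.1.2.1. If the gate holds back part of the local skin reaction, the AE record says less about tolerance than it appears to.

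The SAE form raises a different problem: the causality grade that reaches the sponsor may not be the one the investigator assigned.

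**Working it through.** No arithmetic applies. The documents give no expected AE rate, and the point depends on no alpha, power or sample size. The check takes each kind of event through both routes of Section 7.1.1.

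| Event | Route 1 | Route 2 | Result |
|---|---|---|---|
| (a) Unexpected skin deterioration, judged unrelated to the product | Met | Not met | Recorded; can be graded Unrelated |
| (b) New irritation, expected, possibly product-related, not attributed to baseline | Not met | Met | Recorded; can be ticked Expected |
| (c) Expected skin deterioration attributed to baseline health | Not met | Not met | Not recorded |
| (d) Expected worsening of an existing skin condition, possibly product-related | Not met | Not met, because not new | Not clearly recorded |

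Rows (a) and (b) show that the Unrelated category and the Expected box can each be used. Rows (c) and (d) are the gap. Participants with existing perineal disease are foreseen: the case report form in Appendix 11.5 lists an open perineal wound among the catheter indications.

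The width of the gap depends on what unexpected means in Section 7.1.1.

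- If it has the Section 7.2.3 meaning, an event is unexpected when its nature, severity or frequency departs from the risk information already described. Mild irritation at the cleansing site is described there. Worsening that stays mild then fails route 1; worsening beyond mild would be unexpected on severity and would be admitted.
- If it means unexpected for that patient's clinical course, a listed product reaction could pass route 1. Deterioration that the investigator anticipated from the patient's baseline condition would fail it, whatever its severity.

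The text does not say which is meant, and each reading leaves something out. Under the second, a serious deterioration put down to baseline could never be assessed as an SAE, because Section 7.1.2 considers only AEs.

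The relatedness scales, set side by side:

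| Section 7.2.2 | AE form (11.3) | SAE form (11.4) |
|---|---|---|
| Unrelated | Not Related | Not Related |
| Possible | Possible | Possibly Related |
| Probable | Probable | no box |
| Definite | Definite | Related (definitely) |

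Section 7.2.2 defines Probable by a high degree of certainty of a link, and Possible by a link that seems unlikely but is not excluded. A Probable SAE must therefore be lowered to Possibly Related or raised to Related on the SAE form. The label Possibly Related is also explained differently there, as an event that may be related.

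**The case against.** Several stronger readings are tempting, and the documents do not support them.

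- A reader might infer that Section 7.1.1 contradicts the rule to document events whatever their relationship. It does not: Section 7.2.4 limits that rule to events already defined as AEs or SAEs in Section 7.1. The fair criticism is that the rule has little content for route 2, where relationship has already been used to admit the event.
- A reader might infer that all expected or all unrelated events are lost, including the mild irritation named in Section 7.2.3. Rows (a) and (b) show otherwise. The could-be-related test is also a low bar, since Possible in Section 7.2.2 includes links thought unlikely.
- A reader might take the version 5.0 entry in the document history, that no AEs or SAEs had been reported by then, as a sign of under-recording. It fits a low-risk product equally well, and Section 2.2 reports favourable skin-safety testing. It proves neither.
- A reader might say that only the investigator sees safety data. Sections 7.2.5 and 7.2.6 send AEs to the IRB under its requirements, and SAEs to the sponsor and IRB. That review reaches only events that passed Section 7.1.1.

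It is also fair to say that Section 7.1 presents the narrow definition as a deliberate choice for a marketed product used as labelled. That justifies leaving out new non-skin events judged unrelated. It does not explain why local skin worsening, at the site where the product is applied, should depend on being unexpected.

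On the SAE form, Appendix 11.4 tells staff to add the event to the AE log, and the AE form does carry Probable. The grade can therefore survive elsewhere, but one event may then hold two different grades, and the SAE report remains miscoded.

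**Conclusion.** The point holds in a limited form. Section 7.1.1 applies expectedness or causality before recording, while Sections 7.2.2 and 7.2.3 and the AE form apply them afterwards. Expected worsening of an existing perineal skin condition, even if possibly product-related, and expected deterioration attributed to baseline health may go unrecorded and so cannot become SAEs. This rests on reading the two routes as the complete AE definition, as Section 7.2.5 does. That skin reactions are in fact under-counted is not shown.

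The missing Probable category on the SAE form is a plain mismatch and does not depend on that reading.

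The number of events affected cannot be computed from the documents. The consequence is confined to safety description: AEs are not an endpoint in Section 3, Section 8 has no AE analysis, and AE recording starts with the Educational Intervention, so there is no control-period comparison to bias. The primary CAUTI analysis is unaffected.

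**What to change.** Reconcile Section 7.1.1 with Sections 7.2.2 to 7.2.4:

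- Remove unexpectedness as a condition for recording perineal skin and soft-tissue deterioration, so that any such deterioration is an AE.
- Keep route 2 as it stands for any new condition that could be product-related. Limiting the whole definition to local skin findings would lose the possibly related non-skin conditions that route 2 now captures, along with any SAEs arising from them.
- State that expectedness and relatedness are assigned after recording, under Sections 7.2.2 and 7.2.3.
- Put the four Section 7.2.2 relatedness categories, with the same definitions, on the SAE form.

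The cost is protocol and form wording plus some additional AE forms, mostly for mild events found at inspections already described. Section 7.2.4 asks for a new form at each change in severity, which adds a little more. If the change is made while the study is running, its date should be reported with the AE counts, because counts before and after it would rest on different definitions.

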#### 7.1.2. Definition of Serious Adverse Events (SAE)

Any AE that results in any of the following outcomes: Death, life-threatening event, requires or prolongs inpatient hospitalization, results in persistent or significant disability or incapacity, results in a congenital anomaly or birth defect, results in an important medical or event or requires medical intervention to prevent one of these outcomes. All AEs that are identified as per 7.1.1 will have Investigator determination of SAE and will have documented appropriate medical care for the event available in the EHR.

### 7.2. Classification of an Adverse Event

#### 7.2.1. Severity of Event

The severity of all adverse events will be graded on a scale of one through five according to the most recent version of the Common Terminology Criteria for Adverse Events guideline, where each grade represents a unique clinical description based on this general guideline:

- **Grade 1:** Mild; asymptomatic or mild symptoms; clinical or diagnostic observation only; intervention not indicated.
- **Grade 2:** Moderate; minimal, local or noninvasive intervention indicated; limited age-appropriate instrumental activities of daily living.
- **Grade 3:** Severe or medically significant but not immediately life-threatening; hospitalization or prolongation of hospitalization indicated; disabling; limiting activities of daily living involving self-care.
- **Grade 4:** Life threatening consequences; urgent intervention indicated
- **Grade 5:** Death related to AE

#### 7.2.2. Relatedness of Event

All adverse events (AEs) must have their relationship to study intervention assessed by the PI who examines and evaluates the participant based on temporal relationship and his/her clinical judgment. The degree of certainty about causality will be graded using the categories below.

- **Unrelated:** This category applies to those adverse events which, after careful consideration, are clearly and incontrovertibly due to extraneous causes (disease, environment, etc.)
- **Possible:** This category applies to those adverse events for which, after careful medical consideration at the time they are evaluated, a connection with the Investigational Product administration appears unlikely but cannot be ruled out with certainty.
- **Probable:** This category applies to those adverse events which, after careful medical consideration at the time they are evaluated, are felt with a high degree of certainty to be related to the Investigational Product.
- **Definite:** This category applies to those adverse events which, after careful consideration, are clearly and incontrovertibly due to the Investigational Product.

#### 7.2.3. Expectedness

The PI will be responsible for determining whether an AE is expected or unexpected. An AE will be considered unexpected if the nature, severity, or frequency of the event is not consistent with the risk information previously described for the study intervention. One AE that may occur during the study is mild irritation at the cleansing site.

#### 7.2.4. Relatedness of Event Time Period & Frequency of Event Assessment and Follow-Up

All AEs and SAEs will be captured on the appropriate reporting form. Information to be collected includes event description, time of onset, clinician's assessment of severity, relationship to study product (assessed only by those with the training and authority to make a diagnosis), and time of resolution/stabilization of the event. All AEs and SAEs as defined in section 7.1 occurring while on study must be documented appropriately regardless of relationship. All AEs will be followed to adequate resolution.

Changes in the severity of an AE will be documented to allow an assessment of the duration of the event at each level of severity. Changes in severity will necessitate a new CRF to document the new level of severity. AEs characterized as intermittent require documentation of onset and duration of each episode.

The PI will record all reportable events with start dates occurring any time after the start of the Educational Intervention through the end of the study or resolution of the AE/SAE, whichever is later.

#### 7.2.5. Adverse Event Reporting

All non-serious AEs as per 7.1.1 will be recorded on the Adverse Event form (Appendix 11.3), and reported to the IRB as per IRB reporting requirements.

#### 7.2.6. Serious Adverse Event Reporting

The study investigator shall complete an SAE Form (Appendix 11.4) and submit to the study sponsor and to the reviewing Institutional Review Board (IRB) as soon as possible, but in no event later than 48 hours after the investigator first learns of the effect. The study sponsor is responsible for conducting an evaluation of the SAE and shall report the results of such evaluation to the Food and Drug Administration (FDA) and to all reviewing IRBs within 10 working days after the sponsor first receives notice of the effect. Thereafter, the sponsor shall submit such additional reports concerning the effect as FDA requests.

## 8. STATISTICAL CONSIDERATIONS

### 8.1. Sample Size Determination

The primary outcome will be measured as number of CAUTIs per 1000 catheter days. Given this type of data, a Poisson regression model will be used to model CAUTI incidence, with the dichotomous predictor variable pertaining to the intervention serving as the critical test for the hypothesis. To determine how many catheter days would be needed to adequately power the study, a power analysis was conducted using G\*Power 3.1.9.2, with the following parameters:

- **Baseline CAUTI Rate:** 0.89/1000 catheter days (entered as .00089/day)
  - Baseline rate reflects CAUTI rate for NorthShore University Health System in 2016.
- **Hypothesized reduction in CAUTI:** 50%
- **Alpha:** 0.05 (one-tailed)
- **Power:** 80%
- **Mean Exposure:** 1 day (the actual exposure will vary by participant, but entering 1 day can be used to determine number of catheter days rather than number of participants).
- **R^2 other X:** 0%
- **X distribution:** Binomial
- **X parm II:** 0.5

The result from this analysis indicated that 83,426 catheter days would be needed to adequately power the study at 80%. NorthShore Hospital University System averages approximately 32,000 catheter days annually, which can be reduced to 2,667 per month. Thus, total number of catheter days required for collecting retrospective data and prospective data would be 85,344 catheter days. The 42,672 (85,344-catheter days/2) catheter days of prospective data in comparison to a similar number of catheter days of retrospective data will provide data required for conducting the analysis.

## 8.2. Statistical Analysis

### 8.2.1. Primary Endpoint

The primary endpoint will be the comparison of CAUTI rates during the intervention period compared to the retrospective control period. This will be tested by modeling the likelihood of developing a CAUTI as a function of intervention status using Poisson regression, with the number of catheter days serving as the offset. A significant value for the parameter representing the intervention will serve as the test for the impact of the intervention. Formally, the hypothesis is:

$$H_0: \beta_1 \geq 0$$

$$H_1: \beta_1 < 0$$

Where  $\beta_1$  represents the beta-parameter for the dichotomous predictor variable pertaining to the intervention, with the retrospective control group coded as 0 and the prospective intervention group coded as 1.

The 95% confidence interval for the incidence rate ratio will also be presented.

Given that the retrospective and prospective portions of the study cover a significant period of catheter days, it is not expected that the two groups will vary on demographic variables or other key variables such as length-of-time the catheter is inserted, hospital unit during admission, etc. Thus, testing the incidence rate ratio will be sufficient for determining if there is a significant difference in the CAUTI rate between the two time periods.

In the event of over-dispersion of the data, negative binomial regression may be implemented to account for the over-dispersed data. Missing data on the primary endpoint is not anticipated to be a concern, given that government reporting requirements dictate that CAUTI rates be reported, which only requires an analysis of catheter days and number of CAUTIs. Participants who are discharged with an IUC or who expire during their admission will have their catheter days as well as any infections that occurred prior to discharge or death counted in the analysis.

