## **4. STUDY DESIGN AND INTERVENTION**

### **4.1. Overall Design**

This is an open-label, superiority study intended to determine if IUC care and maintenance with a prepackaged cloth and standardized cleansing process (ReadyCleanse® Meatal and Perineal Cleansing Cloth) can reduce CAUTI relative to standard-of-care. Four northern suburban Chicago acute-care hospitals, all within the same system (NorthShore University Health System), will implement ReadyCleanse® as the standard-of-care for catheter care and maintenance. An initial training period of six weeks will first occur, during which medical staff will be trained on the appropriate use of the product, and have several weeks to become accustomed to it. Following this six-week training period, data will be collected on incidence of CAUTI prospectively for the duration until all expected catheter days (42,672) have been completed. The incidence rate of CAUTI during the intervention period will be compared to the incidence rate for a similar number of catheter days prior to the six-week training period. A significant reduction in CAUTI rate during the intervention period will be taken as evidence of the ReadyCleanse® cloths and standardized cleansing process likely reducing CAUTI. The end of the study will coincide with the 42,672 catheter days, at which point the study should be adequately powered (see Section 8).

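### Does the 95% confidence interval in Section 8.2.1 leave the one-sided primary test without a clear decision rule?

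*Combined protocol and SAP*

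**What the plan says.** Section 8.1 describes a Poisson regression of CAUTI incidence and makes the intervention indicator the term on which the hypothesis is decided. Its parameter list gives alpha as "0.05 (one-tailed"), power of 80%, a baseline rate of 0.89 per 1000 catheter days and a 50% reduction. The result is that "83,426 catheter days would be needed to adequately power the study at 80"%.

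Section 8.2.1 specifies the same Poisson model with an offset for catheter days, and states H0: β1 ≥ 0 against H1: β1 < 0, with control coded 0 and intervention coded 1. On the decision it says: "A significant value for the parameter representing the intervention will serve as the test for the impact of the intervention". On the interval it says: "The 95% confidence interval for the incidence rate ratio will also be presented". Later, when explaining why no adjustment for patient characteristics is planned, it calls the rate-ratio test "sufficient for determining if there is a significant difference in the CAUTI rate between the two time periods".

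Section 4.1 links the result to the conclusion: "A significant reduction in CAUTI rate during the intervention period will be taken as evidence" that the cloths and cleansing process probably lower CAUTI.

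**The concern.** An analyst working only from Section 8.2.1 finds the word significant but no significance level. The one percentage there is the 95% of the interval. If that interval is two-sided, as is usual, its upper limit falls below 1 only when the one-sided p-value is below 0.025, which is stricter than the 0.05 in Section 8.1. The later phrase about a significant difference has no direction and could be read as a two-sided test.

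If the plan really left this open, a borderline result could be called positive by the test or negative by the interval after the data were seen. The power would also be in doubt: a study sized for one-sided 0.05 has less than 80% power when judged at one-sided 0.025.

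**Working it through.** **Inputs.** From Section 8.1: control rate λ0 = 0.00089 per day, rate ratio 0.5 (so λ1 = 0.000445), one-sided alpha 0.05, power 80%, and 42,672 days per period. Section 8.1 promises only a similar number of retrospective days; equal days are assumed here.

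**The plan's own figure.** The rate-difference formula for total days is

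N = 2 (zα + zβ)² (λ0 + λ1) / (λ0 − λ1)²

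- One-sided 0.05: 2 × (1.645 + 0.842)² × 0.001335 / 0.000445² ≈ 83,360, which is 0.08% below the stated 83,426.
- A two-proportion calculation, also one-sided, gives 83,304, which is 0.15% below.
- Two-sided 0.05 by the same two methods gives 105,828 and 105,756.

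The stated figure therefore fits a one-sided 0.05 test. One two-sided variant, with the null variance taken at the baseline rate, gives 83,671, so the number alone does not prove the sidedness. The explicit wording in Section 8.1 does.

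**How often test and interval part.** Expected events are 42,672 × 0.00089 = 37.98 in control and 37.98 × rate ratio under intervention. Enumerating pairs of independent Poisson counts, with z = log(IRR) / √(1/x1 + 1/x0), gives:

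| True rate ratio | P(one-sided p < 0.05) | P(two-sided 95% CI below 1) | Difference | Share of significant results |
|---|---|---|---|---|
| 0.5 | 0.8152 | 0.7118 | 0.1034 | 12.7% |
| 0.6 | 0.6210 | 0.4899 | 0.1311 | 21.1% |
| 0.7 | 0.4074 | 0.2865 | 0.1209 | 29.7% |
| 1.0 | 0.0487 | 0.0239 | 0.0248 | about 51% |

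The planned test delivers 81.5% power at the design effect and a size of 4.87%. The 51% in the last row is a share of those false positives: 0.0248 out of 0.0487. It is not additional error.

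**What the overlap looks like.** With 38 control events and equal days:

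| Intervention events | IRR | One-sided p | 95% CI | One-sided 95% upper bound |
|---|---|---|---|---|
| 22 | 0.579 | 0.021 | 0.342 to 0.979 | 0.900 |
| 23 | 0.605 | 0.029 | 0.361 to 1.016 | 0.935 |
| 24 | 0.632 | 0.039 | 0.379 to 1.053 | 0.970 |
| 25 | 0.658 | 0.052 | 0.397 to 1.090 | 1.005 |

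For 23 events: log(23/38) = −0.502, SE = √(1/23 + 1/38) = 0.264, z = −1.90, p = 0.029, and the upper limit is exp(−0.502 + 1.96 × 0.264) = 1.016. Only counts 23 and 24 separate test from interval. The one-sided 95% bound agrees with the test in every row.

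**What the text settles.**

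- *Level:* 0.05, one-sided, in Section 8.1, in the same subsection that makes the intervention term decisive.
- *Direction:* H1: β1 < 0 in Section 8.2.1, consistent with the significant reduction named in Section 4.1.
- *Deciding quantity:* the model parameter. Section 8.2.1 gives it the role of the test.
- *Interval:* presented as well, after the test has been named, and without any condition. It has no part in the decision and cannot be left out when it includes 1.
- *Significant difference:* this phrase closes the argument for an unadjusted comparison. It does not replace the formal hypotheses a few lines above it.

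**The case for a change.** The strongest case for acting is this. The study is open-label, the retrospective CAUTI rate is already in hand (Section 6.3.1.2), and the sponsor oversees the final analysis (Section 9.1.7.1). In that setting, the treatment of a borderline result should be beyond argument before the prospective count is known. A reader who took the 95% interval as the rule would be using a criterion with about 71% power instead of about 81%, and might call a result negative that is positive under Section 8.1.

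Part of this stands. Section 8.2.1 does not repeat the level, does not say whether the interval is two-sided, and offers no sentence for the case where the interval includes 1. A cross-reference to Section 8.1 would do no harm. But the lower power belongs to a rule the plan does not contain. Nor is the primary conclusion left to be worded afterwards: Section 4.1 says what a significant reduction will be taken to show, and goes on to commit the conclusions to the intervention as a whole, in view of the retrospective control. What remains open is a supplementary remark about an interval that every reader will see anyway.

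**Conclusion.** The concern does not hold. Followed as written, the plan gives one decision rule: a one-sided test of the intervention parameter at 0.05, with the 95% interval for the rate ratio reported beside it. That rule has a size of 4.87% and 81.5% power at the design effect, in line with the stated 80%. The separation between test and interval (10.3% of studies at a rate ratio of 0.5, 13.1% at 0.6, 12.1% at 0.7, 2.5% at no effect) is real, but it follows whenever a one-sided 5% test is shown with a two-sided 95% interval. It is not a contradiction in this plan. Restating the level or labelling the interval would change no decision, error rate, sample size or power.

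The separation figures assume a two-sided interval, Wald inference, equal days in both periods, the design rates and no over-dispersion. With a one-sided 95% bound the separation would be zero. The conclusion about the decision rule depends on none of these assumptions, only on reading Sections 4.1, 8.1 and 8.2.1 together.
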